### 3.2.6 Cross-over Regimen for Patients Who Recur in the Lung While On-Study

Patients who recur in the lung while on study, and who are thought to be amenable to complete surgical resection of the recurrent tumor will be unblinded. Those patients who were receiving placebo will then have the option of undergoing surgical resection; if fully resected they will be given the option to begin oral therapy with Saracatinib.

Saracatinib will be administered as a once daily, oral dose of 175 mg, for a 28-day cycle, with no breaks between cycles. The duration of treatment with saracatinib will be thirteen 28-day cycles (364 days total). Cycle 1 Day 1 must commence no later than 6 weeks after the time of the definitive metastasectomy. Patients who cannot commence oral therapy within 6 weeks will be removed from the study.

Biological studies to determine the etiology of recurrent osteosarcoma are an important component of this protocol. Prior to metastasectomy, every attempt should be made to

insure that the tumor sample is handled properly, so that all of the biological studies can be performed (see Sections 3.6.1 and Operations Manual).

Patients who recur in locations other than the lung while on-study will be taken off study and will not be unblinded.

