## **5.3 Statistical Considerations**

The primary goal of this study is to determine whether the addition of saracatinib to surgery will result in an improvement in progression free survival (PFS). The sample size will be based on being able to detect a 60% relative improvement (from 33% to 53%) in PFS probability at two years. The current 2-year PFS probability is 33%, when a second surgical complete remission is achieved (3). Assuming exponential survival curves, the hazard rate corresponding to this 2-year PFS probability for the control arm is 0.0462, which is defined as approximately a 0.0462 probability of failing each month when the 2-year PFS probability is 33%. If we assume that the 2-year PFS probability may be 53% for the saracatinib arm, the hazard is 0.0265, which then results in a hazard ratio of 1.75. Forty-four patients will need to be randomized in each arm of the study, for a total of 88 patients, over a 48-month accrual period. Follow-up of the last patient randomized must continue for an additional year. Since this study follows a phase II.5 design (35), this provides 80% power to detect a difference between the two resulting actuarial curves with a one-sided 0.10 alpha level log-rank test.

A secondary goal of this study is to determine whether the addition of saracatinib to surgery will result in an improvement in overall survival (OS). The sample size selected to evaluate PFS will also be adequate to detect a 56% relative improvement (from 45% to 70%) in OS probability at three years. The current 3-year OS probability is 45%, when a second surgical complete remission is achieved (3). Assuming exponential survival curves, the hazard rate corresponding to this 3-year OS probability for the control arm is 0.0222, which is defined as approximately a 0.0222 probability of failing each month when the 3-year OS probability is 45%. If we assume that the 3-year OS probability may be 70% for the saracatinib arm, the hazard is 0.0099, which then results in a hazard ratio of 2.24. Evaluation of the 88 patients who are randomized, over the same time frame, will provide 85% power to detect a difference between the two resulting actuarial curves with a one-sided 0.10 alpha level log-rank test.

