As explained in section 3.2.6, a subset of patients who recur while receiving placebo will be given the opportunity to receive saracatinib. Since patients on both arms will have received this agent, although at different times in the natural history of their disease, this may result in a lessening of the difference in survival between the arms compared to the case when only patients on one arm received the agent. However, since development of a recurrence may still be associated with overall survival duration, the magnitude of the impact may be limited.

An additional secondary goal is to determine if the addition of saracatinib to pulmonary metastasectomy, versus placebo and pulmonary metastasectomy, results in an increase in the time to treatment failure (TTF). Any adverse event that results in discontinuation of either saracatinib or placebo will be considered a treatment failure. This includes toxicity, disease progression or death.

Again, the randomized nature of the Phase II.5 study will allow us to determine the actual 2-year PFS and 3-year OS rates in patients who receive surgery and placebo, or surgery in combination with saracatinib.

Patients will be stratified based on the following criteria:

Number of Recurrences: FIRST versus SECOND versus THIRD or MORE

Number of Recurrent Nodules: ONE or TWO versus THREE or MORE

The date that the patient is randomized will be used as the starting date for measurements of overall survival, progression free survival and time to treatment failure. Progressive disease will be defined as recurrence of osteosarcoma based on radiographic evidence or histologic verification of the recurrent lesion.

At the first annual opportunity following the point at which 20 patients per arm have been randomized (40 total) and potentially followed for at least 12 months, an interim evaluation for futility will be performed.

The futility evaluation will be performed as follows. Based upon the full data available at that time, a conditional power analysis will be performed to determine if the trial is

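### The 85% power for overall survival assumes that crossover to saracatinib brings placebo patients no survival benefit; section 5.3 acknowledges the dilution but neither quantifies it nor qualifies the 85%

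*Combined protocol and SAP*

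**What the plan says.** All places are in the combined protocol and SAP.

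- **OS power (5.3).** The 88 patients sized for PFS are said to be enough to "detect a 56% relative improvement (from 45% to 70%) in OS probability at three years". Under exponential survival, "the hazard rate corresponding to this 3-year OS probability for the control arm is 0.0222" per month. That rate comes from a historical series. The saracatinib hazard is 0.0099 and the hazard ratio 2.24. Then: "Evaluation of the 88 patients who are randomized, over the same time frame, will provide 85% power to detect a difference", using a "one-sided 0.10 alpha level log-rank test". No crossover term appears.
- **Crossover (3.2.6; also the Precis, 3.1, 3.5.1, 3.7.1 and 7.4.2).** Patients with a lung recurrence thought resectable are unblinded. Those on placebo may have surgery, and "if fully resected they will be given the option to begin oral therapy with Saracatinib", for thirteen 28-day cycles.
- **The plan's comment on crossover (5.3).** It says that giving the agent to patients on both arms may lessen the survival difference. It then adds that "since development of a recurrence may still be associated with overall survival duration, the magnitude of the impact may be limited".
- **What the trial is said to deliver (5.3).** Randomization "will allow us to determine the actual 2-year PFS and 3-year OS rates in patients who receive surgery and placebo", or surgery with saracatinib.
- **Start of the OS clock.** Section 5.3 uses the randomization date. Section 3.7.1 uses it too, but for cross-over patients starts OS at the first saracatinib dose.

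**The concern.** The 85% describes a trial in which placebo patients never receive the drug. This trial offers it to some of them after recurrence. If saracatinib prolongs life at that point, placebo-arm OS rises and the contrast shrinks.

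The reason given for expecting little impact is that recurrence is related to survival. That is a statement about prognosis. The size of the dilution depends on two other things: how many placebo patients cross over, and what the drug does for them afterwards.

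Two uses of the result are at stake. A null OS result read against 85% power would look like evidence of no survival effect. And section 1.2.9 says the results may supply parameters for a definitive trial; a placebo OS rate that includes later saracatinib would be too high if taken as the rate for surgery alone.

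**Working it through.** **1. Reproduce the 85%.** Inputs from 5.3: 3-year OS 45% and 70%, 44 per arm, 48 months' accrual, 12 months' further follow-up, one-sided alpha 0.10. Uniform accrual and no dropout are assumed.

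- Hazards: −ln(0.45)/36 = 0.0222 and −ln(0.70)/36 = 0.0099; ratio 2.24.
- Expected deaths per arm: 44 × [1 − (e^(−12h) − e^(−60h))/(48h)] = 23.3 and 12.9; total 36.2.
- Freedman: √36.2 × (2.24 − 1)/(2.24 + 1) − 1.2816 = 1.02, power 84.6%.
- Unequal-variance log hazard: ln(2.24)/√(1/23.3 + 1/12.9) − 1.2816 = 1.04, power 85.1%.
- Schoenfeld: √(36.2/4) × ln(2.24) − 1.2816 = 1.14, power 87.3%.
- Simulated log-rank test: about 87%.

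The stated figure is therefore sound, as a no-crossover figure.

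**2. How many placebo patients could cross over.** The documents give no uptake. The pool depends on the window, which they word in two ways: 5.3 speaks of recurrence while receiving placebo (364 days), while 3.2.6 and 7.4.2 speak of recurrence on study.

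- During the 12 months on placebo: 5.3 equates 33% PFS at 2 years with 57.4% at 1 year, so 44 × (1 − 0.574) = 18.7 events.
- By month 60: with PFS hazard 0.0462 in the formula of step 1, 33.8 events.
- Upper guide to uptake: section 1.2.1 reports 512 patients with surgical remission and 291 without, 512/803 = 64%. That gives about 12 crossovers (18.7 × 0.64) or about 22 (33.8 × 0.64).

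**3. Model for OS with recurrence.** Let p be the recurrence hazard and m the death hazard after recurrence, with no death before recurrence:

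S(36) = e^(−36p) + [p/(p − m)] × (e^(−36m) − e^(−36p)).

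- Placebo: p = 0.0462 and S(36) = 0.45 give m = 0.0572.
- Saracatinib: p = 0.0265 and S(36) = 0.70 give m = 0.0354, a ratio of 0.62.
- With p = 0.0265 but m left at 0.0572, S(36) is only about 61%.

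So, within this model, the plan's own 70% needs lower mortality after recurrence as well as later recurrence.

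**4. Power with crossover.** A fraction of placebo recurrences has m multiplied by a factor: 0.75 (weak), 0.62 (step 3) or 1/2.24 (the full stated OS effect). Fraction and factor are both assumptions. Each cell runs from 25% to 64% of recurrences crossing.

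| Post-recurrence factor | Recurrence in the 12 months on placebo | Recurrence at any time |
|---|---|---|
| 0.75 | 84–80% | 82–75% |
| 0.62 | 83–74% | 79–65% |
| 1/2.24 | 79–64% | 73–45% |

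Repeat runs agree to within about 3 points.

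**5. A second model.** Here the placebo death hazard is 0.0222 from randomization and drops at recurrence in those who cross, by the full 2.24 or by half of it on the log scale. The recurrence hazard is 0.0240 (0.0462 − 0.0222) or 0.0462. Without crossover power is 86.6%. With 25% crossing it is 82–85% (12-month window) or 80–84% (any time); with 50% crossing, 76–83% or 71–82%. With no effect after recurrence it stays where it was.

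**6. The placebo OS rate.** In the model of step 3, with 64% crossing, placebo 3-year OS rises from 45% to about 49% (factor 0.62) or 53% (1/2.24) in the 12-month window, and to about 53% or 58% if recurrence at any time counts.

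**The case against.** The case for leaving the text alone is substantial. Section 5.3 discloses the dilution in the paragraph directly after the power figure, and compares it with the situation in which only one arm gets the drug. OS is secondary; PFS sizes the trial, and crossover follows the PFS event. No document supplies an uptake or a post-crossover effect. The 64% is surgical remission in general relapse series. Crossover here also requires recurrence confined to the lung after an earlier resection, complete re-resection, the patient's choice and a start within 6 weeks. The factor 0.62 is what the model needs to reach 70%; it is not an observed drug effect.

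All of that stands, and it rules out three stronger readings that a reader might infer.

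- *That the plan overlooked crossover.* It did not. The gap is the missing size, beside an unqualified 85%.
- *That the OS comparison is underpowered by a known amount, for example 60% to 80% power with about 22 of 44 placebo patients crossing.* That rests on the widest window and on assumed inputs. Under the narrower window and a weak effect, power stays at 80% or more.
- *That placebo 3-year OS is not identified.* As-randomized placebo OS, including optional later saracatinib, can be estimated by Kaplan-Meier. What cannot be identified without further assumptions is 3-year OS had no placebo patient received saracatinib, which is what the historical 45% represents.

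Disclosure in words does not settle the point, because the reason offered for a limited impact says nothing about uptake or effect.

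**Conclusion.** The concern holds in a conditional form. The 85% is correct only if crossover brings placebo patients no survival benefit; if saracatinib works after recurrence, it is an upper bound. Over the assumed ranges the loss from about 87% runs from about 3 points (87 − 84) to 23 points (87 − 64) if only recurrence on placebo leads to crossover. It runs from about 5 (87 − 82) to 42 points (87 − 45) if recurrence at any time does, the far end needing both the highest uptake and the full stated effect. With low uptake or little effect it is small. Primary PFS power is untouched.

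The OS definition needs tightening as well. Section 3.7.1 does not say whether the restarted clock for cross-over patients replaces the randomized comparison or adds to it. Until it is reconciled with 5.3, even the as-randomized placebo rate is ambiguous.

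**What to change.** In section 5.3:

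1. Label the 85% as assuming no crossover effect. Add a power range beside it, with uptake, post-recurrence effect and both crossover windows stated as assumptions.
2. Delete or qualify the remark that the impact may be small.
3. State that OS is compared as randomized, from the randomization date, for saracatinib versus placebo with optional saracatinib after resected lung recurrence. Reword the promise of actual 3-year OS rates to match. Reconcile the OS start date for cross-over patients in 3.7.1 with 5.3.

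A supportive crossover sensitivity analysis is optional, and its method is best left to the sponsor: with about 36 deaths, a model-based adjustment such as a rank-preserving structural failure time model would be imprecise.

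The cost is wording, and a stated OS power that looks less favourable. No extra patients or data are needed.

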### **3 Study Implementation**

#### **3.1 Study Design**

The primary objective of this study is to determine whether pulmonary metastasectomy and treatment with saracatinib, versus pulmonary metastasectomy and treatment with placebo, results in an increase in progression free survival. A secondary objective is to determine whether pulmonary metastasectomy and treatment with saracatinib, versus pulmonary metastasectomy and treatment with placebo, results in an increase in overall survival. Patients will be eligible for the study following the histological verification of recurrent osteosarcoma. Patients will be stratified based on the number of recurrences (FIRST versus SECOND versus THIRD or MORE) and the number of recurrent nodules (ONE or TWO versus THREE or MORE).

Randomization will occur following complete resection of all lung nodules and the histological verification of recurrent osteosarcoma.

Patients who are randomized to the saracatinib arm will receive saracatinib, 175 mg, orally, once daily, for a 28-day cycle, with no breaks between cycles. The total duration of treatment with saracatinib will be **thirteen 28-day cycles** (364 days total). Patients will receive one 125 mg tablet (9.5 mm diameter) and one 50 mg tablet (7 mm diameter).

Patients who are randomized to the placebo arm will receive placebo, orally, once daily, for a 28-day cycle, with no breaks between cycles. The total duration of treatment with placebo will be **thirteen 28-day cycles** (364 days total). Patients will receive one 9.5 mm tablet and one 7 mm tablet. These tablets will be indistinguishable from saracatinib.

Patients who recur in the lung while on-study and who are thought to be completely resectable will be unblinded. Those patients who were receiving placebo will be offered the opportunity to undergo additional surgical resection, followed by treatment with Saracatinib. If fully resected, they will then begin oral therapy with saracatinib. Saracatinib will be administered as a once daily, oral dose of 175 mg, for a 28-day cycle, with no breaks between cycles. The duration of treatment with saracatinib will be thirteen 28-daycycles (364 days total).

Patients will be followed for the duration that this study is open. If accrual rates proceed as projected, the total duration of this study will be six years.

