unlikely to find an effect at the 0.10 one-sided level with continued accrual, based on the PFS endpoint. Since the goal is to detect a difference between two year PFS of 33% and 53%, an early evaluation will be performed based on the binomial probabilities at the 12-month point, which reflect the same objective. A PFS of 33% at 2 years would be equivalent to a 1 year PFS of 57.4% and a PFS of 53% at two years is equivalent to a 1 year PFS of 72.8%. Using these as the values under the alternative, and using the actual proportions without progression at 1 year based on the observed fractions based on the expected sample size at 1 year, the conditional power of the trial assuming accrual of however many patients would remain to be entered will be computed. If the conditional probability of finding a difference at the one-sided 0.10 level at the end of the trial is less than 20%, then it will be reasonable to recommend that no further patients will be enrolled. Alternatively, an evaluation based on exponential distribution of PFS may be substituted for the binomial evaluation.

At the first annual point after which 30 patients per arm (60 total) have been accrued and potentially followed for at least 12 months, a very stringent interim monitoring rule will be used to determine if superiority is identified early. If at this single interim efficacy evaluation for superiority, the log-rank p-value for the difference (one-tailed) is  $<0.001$ , then accrual will stop. Otherwise, enrollment will continue as planned.

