### 5.5 Data and Safety Monitoring Plan

The SARC Executive Committee will convene monthly via teleconference to review with the study principal investigator the study accrual, adverse events, serious adverse events, protocol violations and/or deviations. Data provided to this committee will be blinded as to the treatment arm for the events reported. Any concerns related to patient safety will be referred to the NCI DSMB as they will have access to unblinded data.

A NCI-created DSMB will monitor this trial for toxicity, as well as clinical endpoints relative to early termination, in its annual meetings. As noted above (see Section 5.3), clinical evaluations of endpoints will be formally evaluated beginning after 40 to 60 total patients have accrued and potentially followed for 12 months.

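### Does the superiority look come too late to matter, when stopping accrual is its only stated consequence?

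*Combined protocol and SAP*

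**What the plan says.** Section 5.3 plans randomization "for a total of 88 patients, over a 48-month accrual period", and adds: "Follow-up of the last patient randomized must continue for an additional year". The final PFS analysis therefore falls at about month 60.

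The same section sets "a very stringent interim monitoring rule will be used to determine if superiority is identified early". It is timed "At the first annual point after which 30 patients per arm (60 total) have been accrued and potentially followed for at least 12 months". The criterion begins "If at this single interim efficacy evaluation for superiority, the log-rank p-value for the difference (one-tailed) is" and sets the threshold below 0.001. The action is "then accrual will stop. Otherwise, enrollment will continue as planned". No other consequence of crossing is given there.

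Two other places bear on this. Section 5.5 has the DSMB monitor toxicity "as well as clinical endpoints relative to early termination, in its annual meetings". Section 3.1 gives a longer horizon than section 5.3: "If accrual rates proceed as projected, the total duration of this study will be six years".

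**The concern.** A rule meant to act on early superiority should have something left to act on. On the stated accrual plan, the condition of 60 patients with a year of potential follow-up is met when enrolment is almost over, and the look then waits for an annual point. If that point is month 48, the two branches of the rule are the same, because no accrual remains to be stopped or continued.

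The text would then leave the DSMB and sponsor without a written next step after a striking result. The final analysis would be about a year away and some patients would still be on blinded treatment. At stake would be a few enrolments and the timing of a result, not the validity of the final comparison.

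**Working it through.** **Inputs.** From section 5.3: 88 patients, 48 months of accrual, 12 months of further follow-up, PFS hazards 0.0462 and 0.0265 per month (hazard ratio 1.75), one-sided 0.10 log-rank test, 80% power, interim threshold 0.001 (z = 3.09). Assumed, because the documents do not say: uniform accrual and no dropout.

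**The plan's own power.** Exponential PFS with analysis at month 60 gives 33.8 + 25.9 = 59.7 expected events. Power = Φ(½√59.7 × ln 1.75 − 1.282) = Φ(2.162 − 1.282) = 81%. The Freedman formula gives 79.6%. The stated 80% is reproduced.

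**Timing of the look.**
- Rate: 88/48 = 1.833 per month.
- 60th patient: 60/1.833 = month 32.7. Adding 12 months gives month 44.7.
- Enrolled then: 60 + 12 × 1.833 = 82, so 6 are left. At month 48, none are left.
- If the annual meeting is equally likely at any time in the 12 months after the trigger, the chance that accrual is still open is 3.27/12 = 27%. The average number left is (3.27²/2 × 1.833)/12 = 0.8.

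**Other uniform accrual periods, same method.**

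| Accrual (months) | Trigger month | Left at trigger | Left at next study anniversary | Chance accrual open, random meeting date | Average left, random meeting date |
|---|---|---|---|---|---|
| 36 | 36.5 | 0 | 0 | 0% | 0 |
| 48 | 44.7 | 6 | 0 | 27% | 0.8 |
| 60 | 52.9 | 10 | 0 | 59% | 3.1 |
| 72 | 61.1 | 13 | 0 | 91% | 6.1 |

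For 60 months: gap 60 − 52.9 = 7.09 months; 7.09/12 = 59%; (7.09²/2 × 1.467)/12 = 3.1. This case fits the six years of section 3.1 less one year of follow-up. Accrual over 96 months would leave 17 at the trigger and 11 at the next anniversary.

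The shape of accrual also matters. If 60 patients enter by month 24 and 28 over the next 24 months, the trigger is month 36 with 60 + 12 × 28/24 = 74 enrolled and 14 left. A ramp-up within 48 months (cumulative enrolment proportional to t^1.25 or t^1.5) leaves 0 to 2.

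**What an earlier look would buy.** The natural alternative is a look at about 30 events, expected at month 37 with 68 enrolled and 20 left. The chance of crossing at hazard ratio 1.75 is Φ(½√d × ln 1.75 − 3.09), and the observed ratio needed is exp(2 × 3.09/√d).

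| Look | Events d | Chance of crossing | Observed ratio needed | Left to enrol | Expected spared |
|---|---|---|---|---|---|
| 30 events (month 37) | 30 | 6.0% | 3.09 | 20 | 0.060 × 20 = 1.2 |
| Month 44.7 | 40.7 | 9.6% | 2.64 | 6 | 0.096 × 6 = 0.6 |
| Month 48 | 45.4 | 11.4% | 2.50 | 0 | 0 |

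Simulated log-rank tests (10,000 trials) gave 5.4%, 8.3% and 10.2%, close to the formula. At an assumed true ratio of 2.5, simulated crossing was 25% with about 16 left, 35% with 6 left, and 41% with none left. Expected spared is then 0.25 × 16 = 4.0 against 0.35 × 6 = 2.1 and 0.

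**The case for a change.** The strongest case for a change concerns the missing next step more than the patients spared. Crossing is not negligible: about 10% to 11% at the design effect and 35% to 41% at a ratio of 2.5. At month 48, 22 patients would have entered in the preceding year. The protocol hazards imply that about 18 of them would be progression-free (11 × 0.768 + 11 × 0.857 = 17.9), so potentially still within their 364 days of blinded treatment. Section 5.3 does not say whether the PFS result would be released or the trial would run on. The futility look shows that a useful time was available: it can come at month 33.8 with 62 enrolled, or month 36 with 66, leaving 22 to 26 patients.

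The gap in the text is real. It does not leave the trial without a route to action. Section 5.5 gives a DSMB with unblinded data a remit over clinical endpoints and early termination, and deciding on release of a result is within the ordinary work of such a board. Stopping accrual also has a consequence beyond enrolment: follow-up runs one year from the last randomized patient, so a stop at month 44.7 would bring its end to month 56.7 instead of 60.

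The contrast with futility does not carry far either. A late, strict efficacy look errs on the side of caution, and section 1.2.9 says that results of this design are not definitive and may serve to plan a later trial. An earlier look would rest on fewer patients with a full year of potential follow-up: those entered by month 25, about 25 × 1.833 = 46, against the 60 now required. Stopping near 68 patients would also reduce information on overall survival, whose 85% power is stated for 88.

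**Conclusion.** No change follows. The arithmetic behind the concern is right under uniform 48-month accrual: the superiority look can spare 0 to 6 patients, most often none. The size depends on that assumption. Slower accrual (60 to 72 months) or front-loaded accrual leaves more patients to spare; ramp-up accrual leaves fewer.

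The timing is a fair trade-off. An event-driven look at about 30 events gains roughly 0.6 of a patient at the design effect and about 2 at a ratio of 2.5. It does so with a lower chance of crossing, a higher observed ratio needed, less mature data and less information on overall survival.

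The unstated consequence of a late crossing is missing detail that the DSMB can settle within its existing remit. Followed as written, the plan still delivers a sound final PFS comparison. The look spends at most 0.001 of one-sided error against 0.10, and the 80% power is reproduced without reference to it.
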